11.4	PRIVACY AND CONFIDENTIALITY	16
12	STUDY FINANCES	16
12.1	FUNDING SOURCE.....	16
12.2	CONFLICT OF INTEREST	16
12.3	SUBJECT STIPENDS OR PAYMENTS	17
13	PUBLICATION PLAN	17
14	REFERENCES	18
15	ATTACHMENTS	18

Study Summary

Title	Evaluation of Tranexamic Acid Prior to Surgery in the Geriatric Hip Fracture Population for the Reduction of Post-Operative Blood Transfusion
Short Title	TAHFT
IRB Number	Please note that this number will be assigned by the IRB and thus will not be in existence at the time of protocol development and initial review.
Methodology	The overall design of the study is a prospective, double-blinded, randomized study in the geriatric hip fracture population comparing those who receive intravenous tranexamic acid prior to incision to those who receive a placebo.
Study Duration	The patient enrollment phase will take approximately 24 months. Study duration for each subject is 3 months. Total study duration is expected to be 36 months, allowing for study start-up before enrollment and data analysis and manuscript writing after completion of study follow-up.
Study Center(s)	Lancaster General Hospital
Specific aims	
Primary:
 
 To compare the percentage of subjects that receive acute post-operative transfusions in the group administered intravenous tranexamic acid compared to the group administered placebo 
Secondary:
 
 To compare length of inpatient hospital stay and the percentage of subjects with readmissions with associated diagnoses within 30 days between the treatment groups To compare rates of complications and mortality within 90 days post hip surgery between the treatment groups
Number of Subjects	The study will enroll approximately four hundred (400) qualified subjects.
Main Inclusion and Exclusion Criteria	
INCLUSION - Eligible subjects will meet ALL the following criteria:
 
 Written informed consent Age \geq 65 years Hip fracture location within the femoral neck, intertrochanteric, and subtrochanteric regions Indication for surgical intervention with one of the following: hemiarthroplasty, total hip replacement, sliding plate and screw fixation, or intramedullary fixation. 
EXCLUSION – Eligible subjects will NOT meet any of the following criteria:
 
 Indication for closed reduction and percutaneous screw fixation Allergy to tranexamic acid Cerebrovascular accident/stroke, active coronary disease/myocardial infarction, or deep vein thrombosis/pulmonary emboli within one (1) month prior to the fracture Presence of hypercoagulable disorder
Intervention	The intervention in the two arms consists of administration of 1) 100 cc normal saline with 1g of tranexamic acid in solution or 2) 100 cc normal saline alone.

Statistical Methodology
	
For assessing the primary endpoint, we will calculate an odds ratio (with a 95% confidence interval) for transfusion with p-values calculated using a likelihood ratio.

Data and Safety Monitoring
	
Monitoring of adverse events will occur every 6 months over the course of the study or more frequently if needed. One interim analysis is planned to assess the primary endpoint for significant efficacy sufficient to stop the trial early. The interim analysis is planned for the ¾ point of the trial or a minimum of 300 subjects enrolled.

Background and Study Rationale

1 Introduction

Geriatric hip fracture patients may significantly benefit from routine administration of tranexamic acid (TXA) prior to the procedure to decrease the risk of blood loss. Thus, this may further reduce the rate of blood transfusions and complications associated with this treatment. With the high volume of geriatric hip fractures treated at Lancaster General Hospital, we would obtain a large patient population to perform an ideal study.

1.1 Background and Relevant Literature

The geriatric hip fracture population is growing throughout the United States secondary to the aging baby boomer population. These fractures require surgical intervention for stabilization and proper rehabilitation. During the 2017 fiscal year, 420 hip fracture operations were performed at Lancaster General Hospital on the geriatric population, and this number has been increasing over the past decade. This population has a significant increase in morbidity and mortality (approximately 50%) within 1 year if the patient does not have an operation within 36 hours of the trauma.^{1,2} Therefore, patients are quickly optimized to a degree where they are safe to tolerate the anesthesia and surgical procedure.

A significant portion of the geriatric hip fracture population have comorbidities including chronic kidney disease, congestive heart failure, ischemic heart disease, stroke, etc.³ These patients may be anemic prior to the surgery, and are at increased risk for further blood loss as a result of the fracture and surgical operation.^{4,5} However, intra-operative or post-operative blood transfusions also increase the risk of infectious and non-infectious complications (i.e. anaphylaxis, acute hemolytic reaction, circulatory overload, metabolic derangements, etc.), cost of admission, and length of stay in this population.⁶⁻⁸ Evidence has demonstrated that postoperative cardiovascular complications are associated with anemia and blood transfusions.⁹⁻¹¹ Therefore, providers must be cautious and aware of risks when deciding if transfusions are indicated for this population.

Tranexamic acid (TXA) is an anti-fibrinolytic medication that has transformed total joint replacement management regarding blood loss prevention. Multiple studies have proven its effectiveness of significantly reducing blood loss during total hip and knee replacement procedures compared to placebo.¹²⁻²⁸ Thus, this medication has drastically reduced the need for post-operative transfusions in this patient population. However, this patient population may be optimized prior to surgery if they have significant anemia because joint replacement surgeries are generally elective and not urgent or emergent.

Geriatric patients requiring emergent hip fracture repair may significantly benefit from routine administration of TXA prior to the procedure to decrease the risk of blood loss. Thus, treatment may

further reduce the percentage of patients who experience blood transfusions and complications associated with transfusions. However, there are only a couple of studies analyzing the use of TXA in the hip fracture population, and these were underpowered.²⁹⁻³¹ Additionally, the American Academy of Orthopedic Surgery and American Association of Hip and Knee Surgeons released guidelines regarding the use of tranexamic acid based on existing literature and clinical evidence.³² They stated the greatest shortcoming in the literature is the lack of high level evidence to support the use of TXA in patients with a history of VTE, myocardial infarction, cerebrovascular event, transient ischemic attack, and/or vascular stent placement. Therefore, they encourage future research to determine the safety of TXA in the high-risk patient.

With the high volume of geriatric hip fractures treated at Lancaster General Hospital (LGH), we aim to obtain a large patient population to perform an ideal study. We would examine if administration of TXA prior to incision in the geriatric hip fracture patient population decreases the risk of intra-operative or post-operative blood transfusions compared to placebo and determine the safety profile of such administration in high-risk patients.

2 Study Objectives

2.1 Primary Objective

The primary objective of the study is to determine if administration of pre-operative intravenous tranexamic acid for surgical geriatric hip fracture subjects reduces the need for post-operative blood transfusions compared to the geriatric hip fracture subjects who are administered placebo.

2.2 Secondary Objectives

A secondary objective is to determine if TXA increases the risk of complications in the geriatric hip fracture population compared to placebo. Complications may include deep vein thrombosis, pulmonary emboli, myocardial infarction, and cerebral vascular events. We also monitor for complications in subjects who do not receive the TXA. We also will look for differences between the groups in 30 day readmission rates.

3 Investigational Plan

3.1 General Design

The overall design of the study is a prospective, double-blinded, randomized study comparing the post-operative rate of blood transfusions in surgical geriatric hip fracture subjects who are administered intravenous TXA prior to incision compared to those who receive a placebo.

Data will be collected at Enrollment, Baseline, Hospital Discharge, and at Follow Up Visits at 2 (two) weeks, six (6) weeks and three (3) months in conjunction with their standard of care post-operative visits. In addition, all unscheduled visits, hospital readmissions, and deaths will also be collected at 6 weeks and 3 months post-surgery.

3.2 Allocation to Interventional Group

Consented subjects are randomized to participate in the study if they meet eligibility criteria. Subjects are randomized in a 1:1 ratio to receive either TXA (intervention), or placebo (control). The randomization will be stratified by the type of procedure:

1. Hemiarthroplasty/total hip replacement
2. Internal fixation with sliding hip screw/cephalomedullary nail

Each stratum will have its own list of random treatment assignments to promote balance in the treatment groups with respect to the stratification factors. The treatment assignments will be computer-generated in blocks of varying sizes using REDCap.

3.3 Study Measures

The following data will be collected from Epic for study purposes:

- Subject demographics (gender, age, race, BMI)
- Hospital admission and discharge dates
- Hospital admission and discharge anti-coagulation medications and fish oil utilization, etc.
- Pre-operative standard of care lab work (CBC, CMP, PT/INR, etc.)
- Type of surgical procedure performed
- Intraoperative hemoglobin/hematocrit (H/H) levels if available
- Post-operative standard of care lab work, days 1 & 2 (CBC, BMP, etc.)
- Number of transfused packed red blood cell units during peri-operative period
- Hemoglobin/hematocrit levels before and after transfusion
- Post-operative DVT prophylaxis
- Length of hospital stay for current hip fracture admission
- Readmission rates within 30 days of hip surgery along with admission diagnosis
- Complications within 90 days of surgery
- Death within 90 days of surgery along with cause of death

3.4 Study Outcomes

3.4.1 Primary Study Outcome

The primary outcome of this study is acute post-operative transfusion of packed red blood cells.

3.4.2 Secondary Study Outcomes

The secondary outcomes of this study include:

- Length of inpatient hospital stay
- Readmission within 30 days post hip surgery along with the associated readmission diagnosis
- Complications within 90 days post hip surgery
- Death within 90 days post hip surgery

4 Study Population and Duration of Participation

Subjects will be recruited from geriatric hip fracture patients acutely admitted through the Lancaster General Hospital Emergency Department and treated by OAL physicians. Consenting subjects will be followed for 90 days post-surgery. Participation ends upon the completion of the 3-month post-operative visit with the OAL provider.

The enrollment phase is projected to take approximately 24 months.

4.1 Total Number of Subjects and Sites

The study enrollment is planned to be 400 subjects who meet eligibility criteria and consent to the study. The study will be conducted at only one (1) site, Lancaster General Hospital.

4.2 Inclusion Criteria

A patient who meets all of the inclusion criteria and none of the exclusion criteria is eligible to participate in this study. Patients are enrolled in this investigation only when they or their legally authorized representative have signed and dated a written Patient Informed Consent.

Inclusion criteria that must be met are the following:

1. Provision of written informed consent
2. Age \geq 65 years
3. Hip fracture location within the femoral neck, intertrochanteric, and subtrochanteric regions
4. Indication for one of the following surgical interventions: hemiarthroplasty, total hip replacement, sliding plate and screw fixation, or intramedullary fixation

4.3 Exclusion Criteria

Patients will be excluded for the following:

1. Indication for closed reduction or percutaneous screw
2. Allergy to TXA
3. Cerebrovascular accident/stroke, active coronary disease/myocardial infarction, or deep vein thrombosis/pulmonary emboli within one (1) month of the fracture
4. Presence of hypercoagulable disorder, including cancer (active disease), elevated blood homocysteine levels, antiphospholipid antibody syndrome and inherited protein deficiencies (antithrombin III, factor V Leiden, protein S & C deficiencies, prothrombin gene mutation)

4.4 Subject Recruitment

Given approximately 75% of the hip fractures in Lancaster County present at Lancaster General Hospital and are operated on by OAL physicians, there is not a need for marketing or advertising to recruit study subjects. OAL's volume of hip surgeries performed in calendar year 2018 was over 300.

Eligible patients based on the above inclusion criteria and not eliminated by the exclusion criteria will be considered potential candidates for the study. Potential subjects will be approached to participate in the TAHFT study in the emergency room department or operating room holding area of LGH prior to hip surgery.

Once enrolled, a subject is expected to comply with the standard follow-up visit schedule.

4.5 Vulnerable Populations

Children, pregnant women, fetuses, neonates, and prisoners are not included in this research study.

The study may include subjects who are not medically or cognitively able to provide consent and authorization for themselves, and people for whom Spanish, Vietnamese, Nepali, or Arabic is their native language. The consent and authorization process for these subjects is addressed in Section 11.2.

5 Study Intervention

The study drug, TXA, is an anti-fibrinolytic. By reducing the conversion of plasminogen to plasmin, it preserves the structure of fibrin and prevents its degradation.

5.1 Intervention Regimen

In joint replacement surgery, TXA is used at a dosage of 1 g in a 100 cc bag of normal saline, administered intravenously within 30 minutes before incision.

5.2 Regulatory Status of the intervention

Intravenous TXA is approved for marketing by the U.S. Food and Drug Administration and is indicated in patients with hemophilia undergoing tooth extraction to reduce blood loss and prevent hemorrhage. Pre-operative administration in joint replacement is an off-label clinical use. The use in the TAHFT study will be an off-label research use for which we are requesting the IRB to make a determination on IND exemption. The research is not intended to be reported to the FDA in support of a new indication or a significant change in labeling or advertising of the drug, and it does not involve a route of administration, dosage level, or population that significantly increases the risks associated with TXA.

5.3 Risks

The literature does not demonstrate significant complications with TXA administered intravenously in the surgical orthopedic total joint population. However, these studies have not analyzed this drug

administered to the high risk population, which includes those with recent ischemic cardiac events (myocardial infarctions) or thromboembolic events (cerebrovascular accident and deep vein thrombosis/pulmonary emboli), and patients with hypercoagulable disorders. Because of the uncertainty whether this drug increases the risk of embolic events, we aim to eliminate patients with ischemic cardiac and thromboembolic events within 30 days prior to surgery, and those with hypercoagulable disorders, which are the highest risk patients. However, we plan to include patients with events that occurred more than 30 days prior to surgery with the aim to learn more about these at-risk patients, in accordance with the recommendations of the American Academy of Orthopedic Surgery and the American Association of Hip and Knee Surgeons as previously cited.

As a precaution, a post-operative dose of TXA will not be given to any subject enrolled in this study.

5.4 Potential Benefits

Administration of TXA may decrease the need for post-operative blood transfusions and the complications associated with transfusions and anemia. TXA may also decrease the rate of readmissions especially related to anemia. There are several studies in the literature that support that TXA administration may be beneficial in decreasing post-operative blood loss in major orthopedic surgery.¹⁴⁻²⁸ In addition, there are smaller studies examining the hip fracture population showing potential benefit.^{5, 29-31}

5.5 Randomization

Based on the kind of fracture, the treating surgeon will decide on the type of surgical procedure to be performed. The surgeon will designate the type of procedure in the order placed in Epic for TAHFT study drug.

Upon receipt of the Epic order, a study trained OR pharmacist will log into the REDCap TAFHT database. The pharmacist enters the consented subject's name, MRN, and the designated surgical procedure (stratum). REDCap generates the subject's Study ID and then the stratified randomization assignment to TXA or placebo.

For subjects randomized to the intervention arm, a pharmacy technician prepares a plain 100 cc normal saline bag with 10 cc of 100mg/cc TXA-saline (110 cc total). For subjects randomized to placebo, a plain 100 cc normal saline bag containing an additional 10 cc of saline (110 cc total) will be used. A TAHFT study label with subject MRN will be affixed to the plain 100 cc normal saline bag. A trained study pharmacist confirms the work of the pharmacy technician and confirms the REDCap randomization assignment and appropriate study drug/placebo saline bag preparation. The saline solution and tranexamic acid will be used from the pharmacy available stock.

Upon approval, the pharmacist technician prepares the study treatment to be picked up by anesthesia in the OR pharmacy location. Anesthesia confirms study subject identity, and blinded study drug is administered prior to surgical incision.

5.6 Blinding

Only the trained study pharmacists will not be blinded to treatment assignment. The operating room staff, surgeon, anesthesiology, research coordinator, and research assistant will be blinded for the duration of the study, as will the subjects themselves.

6 Study Procedures and Data Collection

The schedule of data collection is detailed in the table below.

Table 1: Schedule of Study Procedures and Data Collection

	Enrollment	Surgical Period	Hospital Discharge	2 Week FU	6 Week FU	3 Month FU
Days	-1-0d	0	2-4d	14d ± 7d	45d ± 7d	90d ± 14d
Study Procedures						
Inclusion/Exclusion Criteria Check	X					
Informed Consent/ Assent Procedure	X					
Randomization		X				
Study Drug Administration		X				
Data Collection						
Concomitant Medications		X	X	X	X	X
Laboratory Tests (PT/INR, CBC, CMP, H/H)		X	if done	if done	if done	if done
Transfusions Received		X	X			
Post-surgical Subject Assessment			X	X	X	X
Hospital Readmission					X	X
Adverse Event / Unanticipated Problem / Death Assessment		X	X		X	X

6.1 Enrollment

Hip fracture patients will be evaluated for appropriateness of surgery and follow the standardized pre-operative testing protocol, which will include lab tests to evaluate patient safety including complete blood counts, comprehensive metabolic panels, and prothrombin time. More advanced lab testing and medical imaging, i.e. EKGs, troponins, CT scans, MRIs, ECHOs, etc., will be done at the discretion of the treating surgical and medical teams as indicated.

OAL physicians will evaluate X-rays to classify the fracture and determine the surgical procedure.

Study enrollment procedures involve checking inclusion and exclusion criteria and consenting eligible subjects or their legally authorized representatives. For eligible patients, OAL physicians will follow the Informed Consent process described in Section 11.2 to discuss the study purpose, risks, benefits, and alternatives to participation and to address the questions and concerns of patients or legally authorized representatives. After the consent process is complete, the OAL physician will document the consent process within the Epic subject medical record.

The study physicians will track all hip fracture patients who they screened but did not meet eligibility criteria or who refused study participation. Additionally, the Clinical Research Coordinator (CRC) will obtain hospital data on all hip fracture patients from the fracture liaison service. This information,

which will be recorded in a de-identified manner, will allow assessment of the generalizability of study results.

6.2 Surgical Period

The surgical period includes subject randomization and administration of study drug just prior to surgery. The research subject receives appropriate hip fracture surgical intervention based on their fracture pattern and determination by the treating surgeon.

The CRC will review Epic for peri-operative study data including:

- Lab work: CBC (Complete Blood Count), CMP (Comprehensive Metabolic Panel), PT/INR (prothrombin time and International Normalized Ratio)
- Blood transfusions administered peri-operatively
- Hemoglobin/hematocrit (H/H) levels before and after blood transfusions
- Adverse events

6.3 Follow Up

6.3.1 Hospital Discharge

The CRC reviews Epic for post-operative study data including:

- Lab work: CBC (Complete Blood Count), CMP (Comprehensive Metabolic Panel), PT/INR (prothrombin time and International normalized ratio)
- Blood transfusions administered post-operatively
- Hemoglobin/hematocrit (H/H) levels before and after post-operative blood transfusions
- Adverse events

6.3.2 Follow Up Visits

The subject receives routine hip fracture post-operative care per the LGH geriatric fracture program. The post-hospital observational phase will include a minimum of two post-operative follow-up evaluations at two (2) weeks, six (6) weeks, and three (3) months.

The two (2) week, six (6) week, and three (3) month standard of care post hip surgery patient assessment will include evaluation of the following:

- X-rays to evaluate hip fracture and hardware placement
- Dressing check (2 week only)
- Physical therapy progress
- Weight bearing status
- Pain medication management
- Post-operative anti-coagulation management
- Bone density osteoporosis prevention conversation

The CRC conducts a medical chart review at the 6 week and 3 month time points for scheduled and unscheduled office visits a subject has with any provider for the following items:

- Subject assessment by the OAL provider
- Medication changes and updates
- Laboratory tests (if done)
- Hospital readmission and associated diagnosis in the interim since discharge after hip surgery
- Adverse events

If a subject reports visits or hospitalizations outside the LG system, study personnel will request permission to obtain data from the providers or health systems. If a subject is reported to be deceased during the follow-up period, the CRC will record this event in the study database.

6.4 *Unscheduled Visits*

It is anticipated that <5% of subjects require an additional unscheduled visit. Typically additional visits are to evaluate wound healing. Any relevant information from these visits will be captured by the medical chart reviews at 6 weeks and 3 months.

7 *Statistical Plan*

Statistical support will be provided by the Lancaster General Research Institute.

7.1 *Sample Size and Power Determination*

Power calculations are based on the assumptions that 20% of the control group will require transfusion as a result of the hip fracture and surgery, and that use of TXA will reduce that percentage by half to 10%. For 80% power with a two-sided alpha of 0.05, and using a likelihood ratio test, the sample size is calculated to be 200 per group with a 1:1 assignment ratio, or 400 total subjects.

[figure not shown]
7.2 *Statistical Methods*

For assessing the primary endpoint, we will calculate an odds ratio (with a 95% confidence interval) for transfusion with p-values calculated using a likelihood ratio.

As a secondary outcome, daily hemoglobin and hematocrit levels will be assessed using a mixed-effects linear model with adjustment for appropriate covariates. Safety/complication outcomes such as 30-day readmissions, embolic events or other complications will be assessed using appropriate binary or Poisson models. Descriptive statistics using appropriate comparative models will be used to assess homogeneity of demographics and any differences in outcomes between the control and intervention groups.

One interim analysis is planned to assess the primary endpoint for significant efficacy sufficient to stop the trial early. The interim analysis is planned for the $\frac{3}{4}$ point of the trial or a minimum of 300 subjects enrolled. To compensate for one interim and one final analysis, we will employ the O'Brien-Fleming adjustments to significance level criteria with $p < 0.0054$ for the interim analysis and $p < 0.0492$ for the final analysis. Based upon a simulation of our primary outcome, futility will be reached at the interim analysis point if the control group has a 30 (30/150 = 20%) or fewer subjects that have experienced a transfusion and the intervention group has 26 (26/150 = 17.3%) or more subjects that have experienced a transfusion. Even if the remaining 50 intervention subjects to be enrolled experience no transfusions and the transfusion rate remains at 20% in the control group, H_0 will not be rejected.

Futility Boundary Based Upon Control Group Transfusion Rate and Projected Intervention Group Number Transfused

8 Safety and Event Reporting

The study will comply with requirements of the Lancaster General Human Research Protection Program (HRPP) policies regarding reporting of unanticipated problems and adverse events.

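### The primary analysis names no stratum or covariate; pre-specifying the randomisation stratum and pre-operative hemoglobin would cost little and could add power

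*Combined protocol and SAP*

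**What the plan says.** Section 7.2, repeated in the Study Summary, defines the primary analysis in one sentence: "we will calculate an odds ratio (with a 95% confidence interval) for transfusion with p-values calculated using a likelihood ratio". No model terms are listed. Adjustment for covariates is mentioned once in the same section, for the secondary daily hemoglobin and hematocrit model, and those covariates are not named.

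Other sections show what is available before treatment:

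- **Stratum.** Section 3.2: "The randomization will be stratified by the type of procedure", with two levels (arthroplasty and internal fixation). Under Section 5.5 the pharmacist enters the surgeon's designated procedure in REDCap before the assignment is generated. Section 3.3 separately collects "Type of surgical procedure performed", which may differ from what was designated.
- **Pre-operative hemoglobin.** Under Section 6.1 patients "follow the standardized pre-operative testing protocol, which will include lab tests to evaluate patient safety including complete blood counts". Section 3.3 lists the pre-operative blood count among the data taken from Epic.

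Section 1.1 notes that these patients may already be anemic before surgery. It gives no figure for how far that predicts transfusion.

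**The concern.** When randomisation is stratified, the usual practice is to carry the stratum into the primary model. When a strong baseline predictor of a binary outcome is already measured, adjusting for it raises power at no cost in subjects. Pre-operative hemoglobin is a plausible predictor of transfusion, and the plan's own background points that way.

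Two things are at stake. The first is power: the design gives about 81% for a halving of the transfusion rate, which leaves little margin if the true effect is smaller. The second is pre-specification: a primary analysis with no stated terms leaves room to choose covariates after the data are seen.

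**Working it through.** **1. Is the plan's arithmetic that of an unadjusted test?**

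Inputs from Section 7.1: 20% v 10%, two-sided alpha 0.05, 80% power, likelihood-ratio test, 200 per group.

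Pooled-variance formula, with mean rate 0.15:

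n = [1.96 × √(2 × 0.15 × 0.85) + 0.8416 × √(0.20 × 0.80 + 0.10 × 0.90)]² / 0.10² = (0.990 + 0.421)² / 0.01 ≈ 199 per group.

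The asymptotic likelihood-ratio test gives 197. Exact enumeration of the unadjusted likelihood-ratio test at 200 v 200 gives power 0.811, both at 0.05 and at the final criterion of 0.0492. The stated 200 per group reproduces.

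The futility count in Section 7.2 also fits an unadjusted test. With ℓ(k, n) the binomial log-likelihood at k/n,

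G = 2[ℓ(40, 200) + ℓ(x, 200) − ℓ(40 + x, 400)].

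For x = 26: G = 2(−100.080 − 77.277 + 179.148) = 3.58, p = 0.0585. For x = 25, p = 0.041. So 26 is the smallest TXA count that misses 0.0492 against 40/200.

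**2. What would adjustment add?**

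The documents give no strength of association, so these are assumptions: 400 subjects, marginal rates held at 20% and 10%, two equal strata, stratum odds ratio 1.5, normally distributed hemoglobin with a log-linear effect, a single look at alpha 0.05, and 40,000 simulated trials per scenario. Size-equalised means that critical values were set so that both tests have the same type I error; the two entries use a null rate of 20% and of 15%.

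| Hemoglobin OR per SD lower | Nominal power, unadjusted | Stratum only | Stratum + hemoglobin | Size-equalised, unadjusted → stratum + hemoglobin |
|---|---|---|---|---|
| 1 | 0.809 | 0.811 | 0.812 | 0.805 → 0.806; 0.806 → 0.807 |
| 1.5 | 0.814 | 0.817 | 0.823 | 0.818 → 0.823; 0.810 → 0.820 |
| 2 | 0.814 | 0.816 | 0.837 | 0.817 → 0.837; 0.816 → 0.835 |
| 3 | 0.813 | 0.815 | 0.865 | 0.815 → 0.860; 0.809 → 0.860 |

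The size-equalised gains are about 0.1, 0.5 to 1.0, 2 and 4.5 to 5 points. Converted by 400 × {[(1.96 + z₁)/(1.96 + z₀)]² − 1}, where z₀ and z₁ are the normal quantiles of the two powers, they equal roughly 1, 5 to 11, 21 to 22 and 53 to 60 extra subjects. For example, 0.817 → 0.837 gives 400 × 0.055 ≈ 22.

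- If the true effect is a threshold (odds ratio 4 in the lowest 30%) and the model is linear, power goes from 0.817 to 0.830 or from 0.813 to 0.830.
- Adjusted type I error is 0.050 to 0.052 (standard error 0.001).
- Stratum alone at stratum odds ratio 3, size equalised: 0.820 → 0.819 and 0.818 → 0.818, so no real gain.
- A separate simulation (10,000 trials per scenario, stratum odds ratio 1 or 1.65) agrees: about 0.81 → 0.83 at a hemoglobin odds ratio of 1.65, and 0.81–0.82 → 0.85–0.86 at 2.7.

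**3. What would adjustment disturb?**

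*Effect measure.* The odds ratio is non-collapsible. The median adjusted odds ratio is 0.44, 0.43, 0.42 and 0.38 across the four scenarios, against 0.44 unadjusted.

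*Futility text.* Section 7.2 says the null cannot be rejected from 30/150 v 26/150 if no further TXA subject is transfused and control stays at 20%. That holds for the unadjusted test only, because an adjusted p-value is not fixed by counts. That exact path is rare: 0 of 50 has probability 0.9⁵⁰ = 0.5% at a true TXA rate of 10%, and 0.87⁵⁰ = 0.1% at 13%. If the last 50 in both arms vary (control at 20%), the chance of final rejection from the boundary is:

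| True TXA rate | Unadjusted (exact) | Adjusted, hemoglobin OR 1 / 1.5 / 2 / 3 (10,000 draws each) |
|---|---|---|
| 10% | 4.3% | 5.2 / 6.6 / 11.3 / 23.0% |
| 13% | 1.8% | 2.1 / 3.0 / 5.1 / 10.3% |

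**The case against.** The strongest reply is that nothing is broken. The unadjusted test holds its size, the planned power is met, and a benefit of more than about 2 points needs a hemoglobin odds ratio above 2 per SD, which the documents do not support with any figure. That stands, and it is why this is a recommendation and not a correction.

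The sub-1-point gains are also hard to tell from noise. Size-equalised unadjusted power should be nearly constant, yet it runs from 0.805 to 0.818 across scenarios. This stands too: at odds ratios of 1 to 1.5 the gain should be read as close to nothing.

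The stratum term is largely convention. Omitting it does not inflate error; at stratum odds ratio 3 the unadjusted size was 0.046. Agreed: the reason to include it is agreement with the design.

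Low cost can be disputed, because the reported odds ratio becomes conditional while the primary aim compares percentages, and a consistent futility statement has to be reopened. Both are real costs, and the fix has to deal with them. The risk-difference interval may also occasionally disagree with the likelihood-ratio p-value, so the plan must say which one decides.

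Finally, the power simulations are single-look. Power and overall error across the two looks, including the interim criterion of 0.0054, were not simulated under the adjusted model. None of this defends leaving the model unstated.

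**Conclusion.** The point holds as an efficiency and pre-specification improvement. Section 7.2 leaves out two baseline variables that the trial already records. Adjusting for them would change power by roughly 0 to 5 points at 400 subjects for hemoglobin odds ratios of 1 to 3 per SD, with type I error near 5% and no material loss in any scenario examined. The size rests on assumed prognostic strength, equal strata, a log-linear hemoglobin effect and a single look. Confidence in the omission is high; confidence in the size of the gain is moderate at best. The benefit of naming the model in advance does not depend on that size.

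**What to change.** Amend Section 7.2 before any unblinded look:

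1. **Model.** Logistic regression of transfusion on treatment, stratum as randomised (the REDCap entry, not the procedure performed) and continuous pre-operative hemoglobin. Use the likelihood-ratio p-value for treatment as the deciding test, with a profile-likelihood confidence interval, at both the interim and the final analysis.
2. **Hemoglobin value.** The last value drawn before randomisation, from the Epic draw time and the REDCap randomisation time. If red cells were given before randomisation, use the last value before that transfusion.
3. **Missing values.** The mean pooled over both arms, with a missing indicator if more than 5% are missing.
4. **Effect measures.** Label the adjusted odds ratio as conditional. Report a standardised risk difference with a delta-method interval, because the aim compares percentages, and the unadjusted odds ratio as supportive.
5. **Futility.** Re-derive the rule under this model or, if it stays as raw counts, say that it is a guide based on the unadjusted test.

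The details in items 2 and 3 are suggestions; what matters is that some rule is fixed in advance. The cost is a short rewrite of Section 7.2, including the futility text, and two time stamps. There is no new measurement and no change to the sample size. It would be sensible to simulate the two-look error and power of the chosen model before it is finalised.
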